11.8 Health Economics

Not applicable.

11.9 Interim Analyses

[figure not shown]
Not applicable.

[figure not shown]
11.10 Sample Size Justification

Sample size calculation for each of the relevant efficacy endpoints is described below.

Primary Efficacy:

Sample size calculation for the primary efficacy hypothesis on decrease in symptomatology is based on published data (Chalmers 2012). With an assumed SD for paired differences of 10, a sample size of 36/sequence will provide 80% power to detect a difference of 3 at one-sided $\alpha=0.05$.

12 ADVERSE EVENTS AND DEVICE DEFICIENCIES

12.1 General Information

An AE is any untoward medical occurrence, unintended disease or injury, or untoward clinical signs (including abnormal laboratory findings) in subjects, users, or other persons, whether or not related to the investigational medical device (test article). Refer to the Glossary of Terms for categories of AEs and SAEs.

Figure 12-1 Categorization of All Adverse Events

[figure not shown]
[figure not shown]

Figure 12-2

Categorization of All Serious Adverse Events

Any other potentially sight-threatening event may also be considered serious based on the judgment of the Investigator and should be reported appropriately as delineated in Section 12.3.

Device Deficiencies

A device deficiency may or may not be associated with subject harm (ie, ADE or SADE); however, not all ADEs or SADEs are due to a device deficiency. The Investigator should determine the applicable category for the identified or suspect device deficiency and report any subject harm separately.

- Failure to meet product specifications
- Solution cloudy
- Packaging deficit (eg, mislabeled product, tampered seal, leaking bottle/container)
- Suspect product contamination
- Lack of performance

12.2 Monitoring for Adverse Events

At each visit, after the subject has had the opportunity to spontaneously mention any problems, the Investigator should inquire about AEs by asking the standard questions:

- “Have you had any health problems since your last study Visit?”

- “Have there been any changes in the medicines you take since your last study Visit?”

Changes in any protocol-specific parameters and questionnaires evaluated during the study are to be reviewed by the Investigator. Any untoward (unfavorable and unintended) change in a protocol-specific parameter or questionnaire response that is clinically relevant, in the opinion of the Investigator, is to be reported as an AE. These clinically relevant changes will be reported regardless of causality.

12.3 Procedures for Recording and Reporting

AEs are collected from the time of informed consent. Any pre-existing medical conditions or signs/symptoms present in a subject prior to the start of the study (ie, before informed consent is signed) are not considered AEs in the study and should be recorded in the Medical History section of the eCRF.

- All SAEs must be reported immediately (within 24 hours) of the Investigator’s or site’s awareness.
- ADEs that do not meet seriousness criteria and device deficiencies must be reported within 10 calendar days of the Investigator’s or site’s awareness.
- A printed copy of the completed *Serious Adverse Event and Adverse Device Effect* and/or *Device Deficiency* eCRF must be included with product returns.
- Additional relevant information after initial reporting must be entered into the eCRF as soon as the data become available.
- Document any changes to concomitant medications on the appropriate eCRFs.
- Document all relevant information from Discharge Summary, Autopsy Report, Certificate of Death, etc, if applicable, in narrative section of the Adverse Device Effect (for related AEs) and Serious Adverse Event eCRF.

Note: Should the EDC system become non-operational, the site must complete the appropriate paper *Serious Adverse Event and Adverse Device Effect* and/or *Device Deficiency* Form. The completed form is faxed or emailed to the Study Sponsor at [REDACTED] according to the timelines outlined above; however, the reported information must be entered into the EDC system once it becomes operational.

Any AEs and device deficiencies for non-study marketed devices/products will be considered and processed as spontaneous (following the postmarket vigilance procedures) and should be communicated to the device’s/product’s manufacturer as per local requirements.

Study Sponsor representatives may be contacted for any protocol related question and their contact information is provided in the Manual of Procedures that accompanies this protocol.

Further, depending upon the nature of the AE or device deficiency being reported, the Study Sponsor may request copies of applicable portions of the subject's medical records. The Investigator must also report all AEs and device deficiencies that could have led to a SADE according to the requirements of regulatory authorities or IRB/IEC.

12.4 Intensity and Causality Assessments

Where appropriate, the Investigator must assess the intensity (severity) of the AE based on medical judgment with consideration of any subjective symptom(s), as defined below:

Intensity (Severity)

- | | |
|----------|--|
| Mild | An AE is mild if the subject is aware of but can easily tolerate the sign or symptom. |
| Moderate | An AE is moderate if the sign or symptom results in discomfort significant enough to cause interference with the subject's usual activities. |
| Severe | An AE is severe if the sign or symptom is incapacitating and results in the subject's inability to work or engage in their usual activities. |

For every AE in the study, the Investigator must assess the causality (Related or Not Related to the medical device or study procedure). An assessment of causality will also be performed by Study Sponsor utilizing the same definitions, as shown below:

Causality

Related An AE classified as related may be either definitely related or possibly related where a direct cause and effect relationship with the medical device or study procedure has not been demonstrated, but there is a reasonable possibility that the AE was caused by the medical device or study procedure.

Not Related An AE classified as not related may either be definitely unrelated or simply unlikely to be related (ie, there are other more likely causes for the AE).

The Study Sponsor will assess the AEs and may upgrade the Investigator's assessment of seriousness and/or causality. The Study Sponsor will notify the Investigator of any AEs that are upgraded from non-serious to serious or from unrelated to related.

12.5 Return product analysis

Study Sponsor representatives and their contact information are provided in the Manual of Procedures that accompanies this protocol.

Alcon products associated with device deficiencies and/or product related AEs should be returned and must include the Complaint # which will be provided by Study Sponsor after the case is entered in the Study Sponsor's Global Product Complaint Management System (GPCMS).

12.6 Unmasking of the Study Treatment

Masked information on the identity of the assigned medical device should not be disclosed during the study. If the treatment code needs to be broken in the interest of subject safety, the Investigator is encouraged to contact an appropriate Study Sponsor representative prior to unmasking the information if there is sufficient time. Dependent upon the individual circumstances (ie, medical emergency), the code may be broken prior to contact with the Study Sponsor. The Study Sponsor must be informed of all cases in which the code was broken and of the circumstances involved. Additionally, the Study Sponsor may be required to unmask the information in order to fulfill expedited regulatory reporting requirements.

12.7 Follow-Up of Subjects with Adverse Events

The Investigator is responsible for adequate and safe medical care of subjects during the study and for ensuring that appropriate medical care and relevant follow-up procedures are maintained after the study.

The Investigator should provide the Study Sponsor with any new safety information (which includes new AEs and changes to previously reported AEs) that may affect the safety evaluation of the device. For AEs that are unresolved/ ongoing at time of subject exit from study, any additional information received at follow-up should be documented in the eCRFs up to study completion (ie, database lock).

All complaints received after this time period will be considered and processed as spontaneous (following the postmarket vigilance procedures) and should be communicated to the medical device's manufacturer as per local requirements.

The Investigator should also report complaints on non-Alcon products directly to the manufacturer as per the manufacturer's instructions or local regulatory requirements.

12.8 Pregnancy in the Clinical Trial

Pregnancy should be included in the Medical History section of the eCRF when a woman becomes pregnant during the study. Pregnancy is not reportable as an AE; however, complications may be reportable and will be decided on a case-by-case basis.

13 DATA HANDLING AND ADMINISTRATIVE REQUIREMENTS

13.1 Completion of Source Documents and Case Report Forms

The nature and location of all source documents will be identified to ensure that original data required to complete the eCRFs exist and are accessible for verification by the site monitor. If electronic records are maintained, the method of verification must be determined in advance of starting the study. At a minimum, source documents should include the following information for each subject:

- Subject identification (name, sex, race/ethnicity)
- Documentation of subject eligibility
- Date of informed consent
- Dates of visits
- Documentation that protocol specific procedures were performed
- Results of study parameters, as required by the protocol
- Trial medication accountability records
- Documentation of AEs and other safety parameters (if applicable)
- Records regarding medical histories and the use of concomitant therapies prior to and during the study
- Date of trial completion and reason for early discontinuation, if applicable
- Pre-screening Questionnaire Responses
- Manifest Refraction and BCVA (as needed)
- Compliance with study and study regimen
- Planned and unplanned lens replacement dates

It is required that the author of an entry in the source documents be identifiable. Direct access to source documentation (medical records) must be allowed for the purpose of verifying that the data recorded on the eCRF are consistent with the original source data.

Electronic CRFs (eCRFs) will be provided to the sites; only designated individuals may complete the CRFs. The eCRFs will be submitted at regular intervals based upon the clinical trial visit schedule. It is expected that all data reported will have corresponding entries in the source documents and that the Principal Investigator will review the reported data and certify

that the eCRFs are accurate and complete. No subject identifiers should be recorded on the eCRFs beyond subject number, and demographic information.

Deviations from this protocol, regulatory requirements, and GCP must be recorded in the study records. An explanation of the deviation should be included, as applicable. In addition, corrective and preventive action should be identified, implemented, and documented within the study records.

13.2 Data Review and Clarifications

Targeted eCRF data will be reviewed against the subject's source data by the study monitors according to the SDV plan to ensure completeness and accuracy. After monitoring has occurred at the clinical sites and the eCRFs have been submitted, additional data clarifications and/or additions may be needed. Data clarifications and/or additions are documented and are part of each subject's eCRFs.

13.3 Regulatory Documentation and Records Retention

The Investigator is required to maintain up-to-date, complete regulatory documentation as indicated by the Sponsor and the Investigator's files will be reviewed as part of the ongoing study monitoring. Financial information is not subject to regulatory inspection and should be kept separately.

Additionally, the Investigator must keep study records and source documents until the Sponsor provides written approval for their destruction. If the Investigator retires, relocates, or for any other reason withdraws from responsibility of keeping the study records, the Sponsor must be notified and suitable arrangements made for retention of study records and source documents needed to comply with national and international regulations (generally 2 years after discontinuing clinical development or after the **latest** marketing approval).

15 APPENDIX

Not applicable.

**Job Notes:**

This is the original (Version 1.0) Statistical Analysis Plan for this study. This version of the Statistical Analysis Plan is based on Version 1.0 of the study protocol.

**Executive Summary:**

## Key Objectives:

The primary objective is to demonstrate superiority of Opti-Free PureMoist (OFPM) when compared to the subject's habitual multipurpose solution (HMPS) in reducing symptoms of contact lens induced dryness after 30 days of use, based on responses to the CLDEQ-8 (abbreviated Contact Lens Dry Eye Questionnaire).

## Decision Criteria for Study Success:

Success of this study will be based on demonstration of superiority of OFPM compared to habitual MPS in reducing symptoms of contact lens induced dryness after 30 days of use, based on responses to the CLDEQ-8.

## 1 Study Objectives and Design

[figure not shown]
[figure not shown]
### 1.1 Study Objectives

[figure not shown]
The overall objective of this study is to demonstrate the benefit of OFPM compared to non-HYDRAGLYDE multipurpose contact lens solutions in presbyopes currently wearing soft contact lenses and experiencing symptoms of dryness.

#### PRIMARY OBJECTIVE

- To demonstrate superiority of OFPM when compared to the subject's HMPS in reducing symptoms of contact lens induced dryness after 30 days of use, based on responses to the CLDEQ-8.

#### EXPLORATORY OBJECTIVES

[figure not shown]
## 1.2 Study Description

This is a prospective, randomized, crossover (2-treatment, 2-period), observer-masked, and quasi-subject-masked study. The study population will consist of approximately 120 subjects (approximately 8 to 20 subjects per site) to be randomized at approximately 8 United States sites to achieve approximately 110 subjects completed. The enrollment for the study is planned for 6 weeks. The expected duration of subject participation in the study (3 scheduled visits) is  $30\pm 3$  days per study period (up to 66 days total). Upon completing Pre-screening Questionnaire and satisfying the relevant pre-screening criteria, subjects will sign informed consent and then be considered enrolled into the study. Subjects will be randomized at Visit1, after inclusion and exclusion criteria are confirmed.

Each subject will wear their habitual lens brand (following manufacture recommended replacement) on a daily wear basis for  $30 \pm 3$  days using either OFPM or their habitual solution daily to care for their lenses.

The planned visit schedule is depicted in Figure 1.2.-1.

Figure 1.2-1 Flow Diagram of Study

### **1.3              Randomization**

A member of the Randomization Programming group at Alcon who is not part of the study team will generate the randomized allocation schedule(s) for study contact lens solution assignment. Subjects eligible after screening at Visit 1 will be randomized (1:1) to receive either OFPM or HMPS to care for their lenses in Period 1 of the study. For Period 2, the contact lens solution that was not allocated for use in Period 1 will be dispensed.

Randomization will be blocked to ensure a balance of study treatment (lens care sequence) allocation within investigational sites. Randomization will be implemented in an Electronic Data Capture (EDC) system.

### **1.4              Masking**

This study is investigator-masked and subject quasi-masked (masked to test solution brand only), with subjects randomized to the order in which they will use OFPM and their HMPS for 30±3 days each. The Investigator will not be aware of the specific treatment being administered and the subject will not be aware of the brand of the test solution. Excluding the study monitor, Lead CSM, and person responsible for generating the randomization schedule, all Alcon study personnel will also be masked. This level of masking will be maintained throughout the conduct of the study. In the event of a medical emergency where the knowledge of subject treatment is required, an individual Investigator will have the ability to unmask the treatment sequence assignment for a specific subject.

## **1.5            Interim Analysis**

No interim analyses are planned for this study.

## **2            Analysis Sets**

### **2.1            Safety Analysis Set**

The safety analysis set will include all subjects/eyes exposed to the newly dispensed habitual lenses for the study disinfected with at least one study lens product evaluated in this study. Safety analysis will be conducted using the safety analysis set on a treatment-emergent basis. For treatment-emergent safety analysis, subjects/eyes will be categorized under the actual lens care products exposed.

### **2.2            Full Analysis Set**

The Full Analysis Set (FAS) will consist of all randomized subjects who are exposed to at least one of the study lens care products as defined for the Safety Analysis Set. Each subject will be classified according to the respective lens care products in the randomized lens sequence, irrespective of the exposure. FAS will serve as the primary analysis dataset for all efficacy evaluations.

### **2.3            Per Protocol Analysis Set**

The per-protocol (PP) analysis set is a subset of all randomized subjects and excludes all data/subjects which have met any of the critical deviation or evaluability criteria identified in the Deviations and Evaluability Plan. Each subject will be classified according to the respective lens care products in the randomized lens sequence, irrespective of the exposure.

## **3            Subject Characteristics and Study Conduct Summaries**

Demographic information (age, sex, ethnicity, race) will be summarized on the safety, full, and PP analysis sets. Baseline characteristics on habitual lens and lens care information as well as activities, CLDEQ-8, [REDACTED], [REDACTED] [REDACTED] will be summarized on the full and PP analysis sets. Due to the crossover design, demographic and baseline data will be presented by lens care sequence group and overall.

All descriptive summary statistics will be displayed with n and % for categorical data, and with mean, standard deviation, median, minimum, and maximum for continuous data.

[figure not shown]
## 4 Efficacy Analysis Strategy

[figure not shown]
This study defines one primary endpoint [REDACTED]. The Full Analysis Set will serve as the primary set for all efficacy analyses. [REDACTED]  
[REDACTED]  
[REDACTED]

### 4.1 Efficacy Endpoints

#### Primary Endpoint

The primary endpoint is the score (range 0 to 37) from CLDEQ-8, obtained by adding the numerical responses to each of the 8 items, collected at the Day 30 follow up, for each product (Visit 2 and Visit 3).

## **4.2 Efficacy Hypotheses**

### **4.2.1 Hypothesis for the Primary Endpoint**

[figure not shown]
The primary hypothesis to be tested is that OFPM is superior to HMPS in reducing dryness symptomatology as measured by CLDEQ-8.

The null and alternative hypotheses for the primary efficacy endpoint are formulated as follows:

$$H_0: \mu_{(OFP)} - \mu_{(HMPS)} \geq 0$$

$$H_a: \mu_{(OFP)} - \mu_{(HMPS)} < 0$$

where  $\mu_{(OFP)}$  and  $\mu_{(HMPS)}$  denote the mean CLDEQ-8 score for OFPM and HMPS, respectively, at the Day 30 follow-up.

## 4.3 Statistical Methods for Efficacy Analyses

### 4.3.1 Primary Efficacy Analyses

A mixed effect repeated measures model will be fit to test these hypotheses, including terms for lens care solution, period, sequence group, and baseline CLDEQ-8 as fixed effects and subject as a random effect. Lens care difference (OFPM minus HMPS) and the corresponding one-sided 95% upper confidence limit will be provided. [REDACTED]

[REDACTED]

[REDACTED]

[REDACTED]

## **4.5            Interim Analysis for Efficacy**

No interim analysis is planned for the study.

## **5            Safety Analysis Strategy**

### **5.1            Safety Endpoints**

The safety endpoints are:

- Adverse events
- Biomicroscopy Findings
  - Limbal hyperemia
  - Bulbar hyperemia

- Corneal infiltrates
- Other Findings
- Conjunctival staining
- Lid Papillae
- Corneal staining
- Device deficiencies

## 5.2 Safety Hypotheses

There are no formal safety hypotheses in this study. The focus of the safety analysis will be a comprehensive descriptive assessment of safety endpoints listed in Section 5.1.

## 5.3 Statistical Methods for Safety Analyses

The analysis set for all safety analyses is the safety analysis set as defined in Section 2.1. The safety variables will be summarized descriptively.

### 5.3.1 Adverse Events

The applicable definition of an Adverse Event (AE) is in the study protocol. All AEs occurring from when a subject signs informed consent to when a subject exits the study will be accounted for in the reporting.

Analysis and presentation of pre-treatment AEs will be separated from treatment-emergent AEs occurring during the study period. A pre-treatment AE is an event that occurs after signing informed consent but prior to exposure to the study lens care for period 1 and period 2. The period for treatment-emergent AE analysis starts from exposure to the study lens care for period 1 and period 2 until the subject completes or is discontinued from the study.

Descriptive summaries (counts and percentages) for ocular and non-ocular AEs will be presented by Medical Dictionary for Regulatory Activities (MedDRA) Preferred Terms. In addition to an overall presentation of AEs, reports will be generated for special classes of AEs such as treatment-related AEs and serious AEs. AEs leading to study discontinuation will be identified. Presentation of ocular AEs will be by eye.

Individual subject's listings will be provided for both pre-treatment and treatment-emergent AEs.

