Each safety variable will be summarized descriptively. Adverse events (AEs) will be classified as treatment-emergent, based on treatment-specific exposure, or pre-treatment. Count and percentage will be provided by relationship to device, and separate tables will be generated for ocular and nonocular AEs. Counts and percentages in each grade category will be presented for each biomicroscopy parameter. Device deficiencies will also be tabulated. Supporting subject listings describing details of each safety variable will be provided. Listings describing details of AEs reported prior to usage of the study solutions will be presented separately from the safety analysis for the treatment-emergent AEs.

Sample Size Justification:

Sample size calculations for the primary endpoint are summarized below (one-sided $\alpha=0.05$).

Endpoint	Assumptions	Power	N
Primary			
CLDEQ-8	SD=10 (paired differences)	80% Detectable difference=3	36 per each of the 2 crossover sequences

[Redacted]

Sponsor:

Alcon Research, Ltd.
[name]
[name]

Protocol Number: LCO115-P001

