11	Unmasked coordinator to assign/dispense the study lens care solution for Period 1 per randomization scheme. 1) HMPS purchased by the subject or provided by the site –or- 2) Investigational Masked OFPM Kit with Kit #. Educate on instructions for use.
12	Assess and record any adverse events (AEs) that are reported or observed from the time of informed consent (see Section 12).
13	Record any device deficiencies that are observed or reported.
14	Schedule Visit 2 (Period 1 Follow-up) to take place on Day 30 ± 3 days (scheduled 29 (± 3) days after Visit 1. Provide subject with Visit 2 reminder instructions: 
 The subject should bring the used lens case for the study period, along with their dispensed study lens care product used during the study period.

10.2.2 VISIT 2 – PERIOD 1/Day 30 & PERIOD 2/DAY 1

1	Document wear time compliance (days, hours) and lens care compliance. Collect used study lens care product from the subject.
2	Obtain information on any changes in medical health and/or the use of concomitant medications since Visit 1.
3	Have subject complete the Subjective Questionnaire based on lenses worn and study solution used during the 30 day study period (CLDEQ-8, [REDACTED] [REDACTED] [REDACTED])
4	Conduct Snellen VA with worn lenses. For details refer to MOP.
5	[REDACTED]

6	Remove lenses and perform biomicroscopy assessments using slit-lamp examination scales. For details and order of staining procedures, refer to MOP.
7	Perform subjective (manifest) refraction assessment and BCVA assessment (as needed). For details refer to MOP.
8	Assess and record AEs that are observed or reported (see Section 12).
9	Record any device deficiencies that are observed or reported.
10	Dispense a new pair of habitual lenses and perform Snellen VA with new lenses being dispensed at the visit. For details refer to MOP. For two-week replacement lens wearers, provide the subject an extra pair of study lenses for replacement at two weeks. Contact the subject at approximately 15 ± 1 days of the study period to remind the subject to replace their lenses and document date of replacement in the source.
11	Unmasked coordinator to assign/dispense the study lens care solution for Period 2 per randomization scheme. 1) HMPS purchased by the subject or provided by the site –or- 2) Investigational Masked OFPM Kit with Kit #. Educate on instructions for use.

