11.2 Analysis Data Sets

11.2.1 Safety Analysis Set

Safety analyses will be conducted using the safety analysis set on a treatment-emergent basis. The safety analysis set will include all subjects/eyes exposed to the newly dispensed habitual lenses for the study disinfected with at least one study lens product evaluated in this study. For treatment-emergent safety analyses, subjects/eyes will be categorized under the actual lens care product exposed.

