11.7 Safety Analysis

The safety endpoints for this study are AEs, biomicroscopy findings, and device deficiencies.

Descriptive summaries (counts and percentages) for ocular and nonocular AEs will be presented by Medical Dictionary for Regulatory Activities (MedDRA) Preferred Terms. In addition to an overall presentation of AEs, reports will be generated for serious AEs. AEs leading to study discontinuation will be identified. Individual subject listings will be provided, as necessary.

Individual subject listings will be provided for AEs that occur after signing informed consent but prior to exposure to study lens care solutions.

Each biomicroscopy parameter will be tabulated by its grade. For each biomicroscopy parameter, counts and percentages of eyes that experience an increase of ≥ 2 grades from baseline to any subsequent visit will be presented. Baseline is defined as Visit 1. A supportive listing will be generated which will include all biomicroscopy data from the affected visit for those eyes experiencing the increase of ≥ 2 grades, with the following variables: lens care solution, Investigator, subject, age, sex, visit, eye, parameter, baseline value, and value at the visit.

Two listings (prior to exposure of investigational products, and treatment-emergent) of device deficiencies, as recorded on the *Device Deficiency* Form, will be provided. Additionally, each device deficiencies category will be tabulated.

No inferential testing will be done for safety analysis.

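### Does SAP 5.3.1 leave open which solution an adverse event found at Visit 2 is counted under?

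*SAP*

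**What the plan says.** SAP 5.3.1 separates pre-treatment from treatment-emergent adverse events. Pre-treatment events come after consent but "prior to exposure to the study lens care for period 1 and period 2". The treatment-emergent period "starts from exposure to the study lens care for period 1 and period 2 until the subject completes or is discontinued from the study". Neither sentence divides Period 1 from Period 2.

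Attribution to a solution is handled elsewhere:

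- Protocol synopsis, Safety: "Adverse events (AEs) will be classified as treatment-emergent, based on treatment-specific exposure, or pre-treatment".
- SAP 2.1: "subjects/eyes will be categorized under the actual lens care products exposed". Protocol 11.2.1 is almost identical: "subjects/eyes will be categorized under the actual lens care product exposed".
- Both of those sections tie exposure to freshly issued lenses that have been disinfected with a study product. A visit date or the handing over of a bottle is not the criterion.
- Protocol 11.7, on which events are listed as occurring before treatment: "AEs that occur after signing informed consent but prior to exposure to study lens care solutions".

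Protocol 10.2.2 gives Visit 2 the double label "PERIOD 1/Day 30 & PERIOD 2/DAY 1" and sets out its procedures in numbered order.

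**The concern.** The treatment-emergent sentence has one stated end, which is leaving the study. Read alone, it lets the Period 1 solution go on collecting events through Period 2. From Period 2 onward a completer has used both solutions, so the word exposed does not by itself pick one.

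Visit 2 is where this could bite. It is the only scheduled examination after Period 1 exposure begins, and protocol 12.2 has the investigator report clinically relevant changes in study parameters as adverse events. A sign first seen at that slit-lamp examination could carry the Visit 2 date as its onset. If a programmer assigned events by whether onset fell on or after the Period 2 start date, that sign would be counted under a solution the subject had not yet received. Errors of that kind pull the two solutions' counts together and can hide a real difference. The pre-treatment wording in SAP 5.3.1 adds to the doubt, because naming both periods could suggest a second pre-treatment interval before Period 2.

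**Working it through.** The plan gives no figure for this point, so the check sets the sections side by side. Short arithmetic shows what each reading would imply.

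**1. Is the sentence in SAP 5.3.1 a per-solution window?** Protocol 10.2.1 and 10.2.2 put successive visits 29 ± 3 days apart, so 29 − 3 = 26 to 29 + 3 = 32 days.

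| Reading of Period 1 attribution | Length |
|---|---|
| Ends at the switch | 26 to 32 days |
| Runs to study exit | 2 × 26 = 52 to 2 × 32 = 64 days |
| Overlap with Period 2 under the second reading | 26 to 32 days |

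Under the second reading every Period 2 event in a completer would count under both solutions. That does not fit the synopsis, which bases classification on treatment-specific exposure. The paragraph in SAP 5.3.1 has a different job: it separates events before treatment from events after treatment starts. The assignment to a solution is made in SAP 2.1.

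**2. What has the subject been exposed to at Visit 2?** The relevant steps in protocol 10.2.2 are:

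| Step | Procedure |
|---|---|
| 6 | Lenses removed, slit-lamp examination |
| 8 | Adverse events assessed and recorded |
| 10 | New lenses issued, visual acuity taken with them |
| 11 | Period 2 solution handed over |

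At steps 6 and 8 the Period 1 solution is the only study solution the subject has used in the trial. The new lenses are tested at step 10, before the Period 2 solution is handed over, so they cannot yet have been disinfected with it. Under SAP 2.1, Period 2 exposure can begin only after a later cleaning cycle. An on-or-after rule keyed to the Visit 2 date would therefore contradict SAP 2.1, protocol 11.2.1 and the synopsis.

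**3. Which events could carry the Visit 2 date?** Detection and onset differ. Protocol 12.2 asks about health problems since the previous visit, so events reported at Visit 2 may have started at any time in Period 1. Only signs first noticed at the examination, with no earlier onset, are open to the problem. Those signs are also reported outside the adverse event tables. SAP 5.3.2 tabulates each biomicroscopy parameter by grade at baseline and Day 30. It also lists eyes that worsen by 2 or more grades, showing lens care solution and visit.

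**4. What would misfiling do?** Let *n* subjects complete, *n*/2 per sequence, with *a* and *b* events per subject-period on OFPM and HMPS. Let a share *p* of Period 1 events be filed under the next solution.

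- OFPM count = (*n*/2)[*a*(1 − *p*) + *a* + *bp*] = *n*[*a* − (*a* − *b*)*p*/2]
- HMPS count = *n*[*b* + (*a* − *b*)*p*/2]
- Difference = *n*(*a* − *b*)(1 − *p*)

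The documents give no value for *a*, *b* or *p*. Under the exposure rule in step 2, *p* = 0 for events found before step 11, and the difference stays at *n*(*a* − *b*). If the two rates are equal, no value of *p* distorts the comparison.

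**5. Does the pre-treatment wording create a second interval?** If it did, a Period 1 event would be treatment-emergent (after Period 1 exposure) and also pre-treatment (before Period 2 exposure). SAP 5.3.1 presents these as separate categories. Protocol 11.7 and the synopsis place pre-treatment events before any use of the study solutions, which settles the meaning.

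**The case for a change.** The best case for a change is that the dividing point has to be inferred. Attribution by actual exposure is a principle, and after the switch both solutions qualify on the bare words. The Period 2 Day 1 label on Visit 2 invites a date cut, and the documents do not say whether onset time is recorded. A choice left until after unmasking could be made knowing which solution it favours, and one sentence would prevent that.

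Part of this stands. No sentence ends Period 1 attribution. Nor does the plan say how to treat an event that begins in Period 1 and worsens in Period 2, or one that arises between leaving Visit 2 and the first cleaning cycle with the new solution. A clarifying sentence would do no harm.

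It does not show a defect. At the examination itself only one study solution has been used, so the exposure rule gives one answer and leaves little discretion to exploit. The interval between the visit and first use of the new solution is short under daily lens care. Reaching the wrong answer takes a programming rule that appears nowhere in the documents and conflicts with their stated basis.

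**Conclusion.** The concern does not hold as a reason to change the plan. SAP 5.3.1 is loosely worded and omits the dividing point between periods, but SAP 2.1, protocol 11.2.1, the synopsis and the Visit 2 step order supply it. An event found at Visit 2 before the Period 2 solution is dispensed belongs to the Period 1 solution. Pre-treatment means before first exposure to any study solution. This is a gap that analysts fill sensibly.

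No distortion of adverse event counts is shown, and none can be sized, because the documents give neither event rates nor the share of events with onset on the switch date. The reach is small in any case. Protocol 11.7 and SAP 5.2 plan no safety testing, adverse events are listed by subject, and the CLDEQ-8 analysis is unaffected.

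The conclusion assumes that analysts apply the stated exposure basis, and that the data show which events were recorded at Visit 2. A programming specification that cut by visit date alone would depart from SAP 2.1 and should be corrected against it.
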